## FUNDING/SUPPORT

0 unresolved  
comment(s)

If the research is being submitted to, supported by, or conducted in cooperation with an external or internal agency or funding program, indicate below all the categories that apply. [i](#)

☐ Not applicable

## Check All That Apply

- ☐ Grant application pending
- ☒ (HHS) Dept. of Health & Human Services
- ☒ (NIH) National Institutes of Health
- ☐ (CDC) Centers for Disease Control & Prevention
- ☐ (HRSA) Health Resources and Services Administration
- ☐ (SAMHSA) Substance Abuse and Mental Health Services Administration
- ☐ (DoJ) Department of Justice or Bureau of Prisons
- ☐ (DoE) Department of Energy
- ☐ (EPA) Environmental Protection Agency
- ☐ Federal Agencies Other Than Those Listed Here
- ☐ Industry (Other than Pharmaceutical Companies)
- ☐ Internal Grant Program w/ proposal
- ☐ Internal Grant Program w/o proposal
- ☐ National Science Foundation
- ☐ Other Institutions of Higher Education
- ☐ Pharmaceutical Company
- ☐ Private Foundation/Association
- ☐ U.S. Department of Education
- ☐ State

Click applicable listing(s) for additional requirements and information:

- [\(HHS\) Dept. of Health & Human Services](#)
- [\(NIH\) National Institutes of Health](#)
- [\(CDC\) Centers for Disease Control & Prevention](#)
- [\(HRSA\) Health Resources & Services Administration](#)
- [\(SAMHSA\) Substance Abuse & Mental Health Services Administration](#)
- Industry (Other than Pharmaceutical Companies) [[IRB Fee Info](#)-look up "Does the IRB Charge a Fee..."]
- [National Science Foundation](#)
- [\(DoEd\) U.S. Department of Education](#)
- [\(DoJ\) Department of Justice or Bureau of Prisons](#)
- [\(DoE\) Department of Energy Summary](#) and [Department of Energy Identifiable Information Compliance Checklist](#)
- [\(EPA\) Environmental Protection Agency](#)

Other:

Specify the funding source and/or cooperating organization(s) (e.g., National Cancer Institute, Ford Foundation, Eli Lilly & Company, South Western Oncology Group, Bureau of Prisons, etc.):

National Institute for Deafness and Other Communication Disorders

## Add Related Grants

If applicable, please search for and select the OSPA Account number or Electronic Internal Approval Form (eIAF) # (notif #) associated with this IRB application using the "Add Related Grants" button.

If required by your funding agency, upload your grant using the "Grant/Contract Attachments" button.

Add Related Grants

Grant/Contract Attachments

Attach Type	File Name
GrantContract	Research Strategy final.pdf

The research involves use of Department of Defense (DoD) funding, military personnel, DoD facilities, or other DoD resources. (See [DoD SOP](#) and [DoD Summary](#) for details)

☒ Yes ☐ No

Using the "attachments" button (below), attach applicable materials addressing the specific processes described in the DoD SOP.

DOD SOP Attachments

Additional Certification: (If your project is federally funded, your funding agency may request an Assurance/ Certification/Declaration of Exemption form.) Check the following if needed:

☐ Protection of Human Subjects Assurance/Certification/Declaration of Exemption (Formerly Optional Form – 310)

Assurance/Certification Attachments

## OTHER REVIEW COMMITTEES

0 unresolved  
comment(s)

If you check any of the below committees, additional materials may be required with your application submission.

Does your research fall under the purview of any of the other review committees listed below? *[If yes, check all that apply and attach applicable materials using the attachment button at the bottom of your screen.]*

☐ Yes ☒ No

## Additional Information

- ☐ Institutional Biosafety Committee
- ☐ Radiation Safety Committee
- ☐ Radioactive Drug Research Committee
- ☐ Markey Cancer Center (MCC) Protocol Review and Monitoring Committee (PRMC)
- ☐ Graduate Medical Education Committee (GME)
- ☐ Office of Medical Education (OME)

- [Institutional Biosafety Committee \(IBC\)](#) - Attach required IBC materials
- [Radiation Safety Committee \(RSC\)](#) - For applicability, see instructions
- [Radioactive Drug Research Committee \(RDRC\)](#)
- [Markey Cancer Center \(MCC\) Protocol Review and Monitoring Committee \(PRMC\)\\*\\*](#) - Attach MCC PRMC materials, if any, per instructions.
- [Office of Medical Education \(OME\)](#)
- [Graduate Medical Education Committee \(GME\)](#)

Attachments

**\*\* If your study involves cancer research, be sure to select "Cancer Research" in the "Research Attributes" section.** ORI will send your research protocol to the Markey Cancer Center (MCC) Protocol Review and Monitoring Committee (PRMC). The [MCC PRMC](#) is responsible for determining whether the study meets the National Cancer Institute (NCI) definition of a clinical trial and for issuing documentation to you (the investigator) which confirms either that PRMC approval has been obtained or that PRMC review is not required. Your IRB application will be processed and reviewed independently from the PRMC review.

## ADDITIONAL INFORMATION/MATERIALS

0 unresolved  
comment(s)

Do you want specific information inserted into your approval letter? ☒ Yes ☐ No

## Approval Letter Details:

If you wish to have specific language included in your approval letter (e.g., serial #, internal tracking identifier, etc...), type that language in the box below exactly as it should appear in the letter. The text you enter will automatically appear at the top of all approval letters, identical to how you typed it, until you update it. Don't include instructions or questions to ORI staff as those will appear in your approval letter. **If these details need to be changed for any reason, you are responsible for updating the content of this field.**

Aim 5 key stakeholder interviews - consent form, quantitative measures, qualitative interview guide

## Additional Materials:

If you have other materials you would like to include for the IRB's consideration, check all that apply and attach the corresponding documents using the Attachments button below.

- ☐ Detailed protocol  
☐ Dept. of Health & Human Services (DHHS) approved protocol (such as NIH sponsored Cooperative Group Clinical Trial)  
☐ Other Documents

Protocol/Other Attachments

Attach Type	File Name
Other	Fully Executed MOU Aim 2 UKPH CSHCN V12P.pdf
Other	Fully executed MOU Aim 3 UKPH CSHCN V12P.pdf
Other	Safety Protocol - nationwide __ Jan 2023.pdf
Other	Safety Protocol - Kentucky __ Jan 2023.pdf
Other	IRB #45213 Permission to replace ICF.pdf

NOTE: [Instructions for Dept. of Health & Human Services \(DHHS\)-approved protocol](#)

If you have password protected documents, that feature should be disabled prior to uploading to ensure access for IRB review.

To view the materials currently attached to your application, click "All Attachments" on the left menu bar.

**SIGNATURES (ASSURANCES)****0 unresolved  
comment(s)****Introduction**

All IRB applications require additional assurances by a Department Chairperson or equivalent (DA), and when applicable, a Faculty Advisor or equivalent (FA). This signifies the acceptance of certain responsibilities and that the science is meritorious and deserving of conduct in humans. The person assigned as DA *should not* also be listed in the Study Personnel section, and the individual assigned as FA *should* be listed in the Study Personnel section.

For a list of responsibilities reflected by signing the Assurance Statement, refer to ["What does the Department Chairperson's Assurance Statement on the IRB application mean?"](#)

For a detailed illustration of how to complete this section, please review the short online video tutorial ["Signatures \(Assurance\) Section - How to Complete."](#) Otherwise, follow the steps below.

🔗	Stamped Consent Form	Aim 4_Student_BIT scoring consent.pdf		0.187	smcgo0	9/19/2025 1:40:02 PM
🔗	Stamped Consent Form	Aim4_Additional Caregivers_CLEAN_7.15.22.pdf		0.246	smcgo0	9/19/2025 1:40:02 PM
🔗	Stamped Consent Form	Aim 5_Parent interviews.pdf		0.477	smcgo0	9/19/2025 1:40:02 PM
🔗	Stamped Consent Form	Aim 5_Stakeholder interviews_CLEAN 9.18.25.pdf		0.484	smcgo0	9/19/2025 1:40:02 PM
🔗	DataCollection	Form M_9.25.25_CLEAN.docx	Form M clean	0.033	jja233	9/18/2025 7:12:15 PM
🔗	DataCollection	Form M_9.5.25_MARKED.docx	Form M marked	0.034	jja233	9/18/2025 7:11:58 PM
🔗	DataCollection	Stakeholder Interview Guide.docx	Stakeholder interview guide	0.034	jja233	9/18/2025 7:11:25 PM
🔗	DataCollection	Stakeholder AIM FIM IAM.pdf	Stakeholder AIM FIM IAM	0.776	jja233	9/18/2025 7:10:58 PM
🔗	DataCollection	Stakeholder background questionnaire.pdf	Stakeholder background questionnaire	0.775	jja233	9/18/2025 7:10:34 PM
🔗	Informed ConsentParental Permission	Aim 5_Stakeholder interviews_CLEAN 9.18.25.pdf	Aim 5_Stakeholder interviews	0.479	jja233	9/18/2025 7:09:02 PM
🔗	InformedConsent_HighlightedChanges	Aim 5_Stakeholder interviews_MARKED 9.8.25.docx	Aim 5_Stakeholder interviews (tracked changes relative to parent interview consent form)	0.081	jja233	9/18/2025 7:08:18 PM
🔗	DataCollection	Coaches Interview Guide_4.29.25.docx	Parent coach interview guide	0.026	jja233	4/29/2025 8:43:55 AM
🔗	-IRB Authorization Agreement	[name] IAA between UK and KH&V (KH&V relying) (UKY 45213).pdf	Reliance Agreement	0.200	MHO272	3/25/2025 9:59:25 AM
🔗	-IRB Authorization Agreement	Fully Executed SMART IRB IAA UCD-UK - FCU-DHH-45213.pdf	Reliance Agreement	0.182	MHO272	3/25/2025 9:59:01 AM
🔗	-Individual Investigator Agreement	[name] IIA (UKY 45213).pdf	IIA	0.214	MHO272	3/25/2025 9:58:49 AM
🔗	-IRB Authorization Agreement	[name] IAA with UoL (UKY 45213).pdf	Reliance Agreement	0.042	MHO272	3/25/2025 9:58:26 AM
🔗	-Individual Investigator Agreement	UKY IRB 45213_IIA_[name]_Revised.pdf	IIA agreement [name] - fully signed	0.211	jja233	3/21/2025 1:48:50 PM
🔗	-Individual Investigator Agreement	UKY IRB 45213_IIA_[name].pdf	IIA Agreement [name]- fully signed	0.269	ovmo223	2/14/2025 12:59:04 PM
🔗	-Individual Investigator Agreement	UKY IRB 45213_IIA_[name].pdf	IIA Agreement - fully signed	0.229	ovmo223	2/14/2025 12:58:38 PM
🔗	DataCollection	interview guide - parents - clean copy - Copy.docx	Aim 5 - parent interview guide	0.045	jja233	2/13/2025 1:57:03 PM
🔗	Informed ConsentParental Permission	Aim 5_Parent interviews.pdf	Aim 5_Parent Interviews	0.473	jja233	2/13/2025 1:53:31 PM
🔗	DataCollection	BIT transcription sheet_clean.docx	BIT transcription sheet	0.016	jja233	1/10/2025 4:32:06 PM
🔗	Advertising	CHAMPS recruit flyer_students-STAMPED.pdf	Recruitment flyer for student language scoring task	15.850	jja233	1/10/2025 4:27:02 PM
🔗	CoverLetter	Aim 4_Student_BIT scoring consent.pdf	Aim 4 consent cover letter for students (participant signature waived)	0.173	jja233	1/10/2025 4:24:18 PM
🔗	ResearchProcedures	CELF5 Ages 9+.pdf	CELF5 - subtests for 9+ year olds	12.217	jja233	7/31/2024 6:28:56 PM

ResearchProcedures	Satisfaction with Interventionist (SIW) - includes TASC.docx	Satisfaction with Interventionist (SIW) - includes TASC	0.028	jja233	7/31/2024 6:26:10 PM
Advertising	CHAMPS ad-STAMPED.pdf	advertisement for newsletters	1.464	jja233	8/11/2023 11:53:00 AM
Advertising	CHAMPSDHH one page flyer_July 2023 (3)-STAMPED.pdf	Recruitment flyer - PR stamped (with more detailed info similar to brochure, but easier to attach in emails)	0.300	jja233	8/11/2023 11:52:29 AM
Assent	Aim 4 child assent (6yr+)_CLEAN 3.16.23.pdf	Aim 4 child assent CLEAN 3.16.23	0.088	jja233	3/16/2023 8:09:17 PM
Advertising	Facebook ad_CLEAN March 2023.docx	social media updated clean copy	0.021	jja233	3/4/2023 9:05:27 AM
Advertising	Website Content_clean 3.2.23.docx	website content - clean copy 3.2.23	0.037	jja233	3/4/2023 9:04:53 AM
Advertising	Facebook ad_MARKED March 2023.docx	social media updated text	0.023	jja233	3/2/2023 8:14:01 PM
Advertising	Website Content_tracked changes 3.2.23.docx	website content - tracked changes 3.2.23	0.040	jja233	3/2/2023 8:12:45 PM
AddInfoProduct	IRB #45213 Permission to replace ICF.pdf	Correspondence between ORI staff and PI	0.333	ovmo223	2/1/2023 12:51:20 PM
AddInfoProduct	Safety Protocol - Kentucky _ Jan 2023.pdf	Safety protocol for Kentucky families (provided to data collectors or coaches working with large number of Kentucky families)	0.192	jja233	1/26/2023 10:32:39 PM
AddInfoProduct	Safety Protocol - nationwide _ Jan 2023.pdf	Safety protocol updated for nationwide recruitment	0.192	jja233	1/26/2023 10:31:33 PM
DataCollection	Revised parent background questionnaire_CLEAN 10.25.22.docx	Revised background questionnaire CLEAN	0.066	jja233	10/25/2022 6:56:22 PM
DataCollection	Revised parent background questionnaire_MARKED 10.25.22.docx	Revised background questionnaire MARKED	0.070	jja233	10/25/2022 6:56:09 PM
Advertising	recontact flyer.pdf	1/3 page flyer to include with brochure in recontact mailing	0.326	jja233	10/25/2022 6:21:51 PM
Advertising	PUBHLTH-033_brochure-STAMPED.pdf	Recruitment brochure - PR stamped (updated for all remote data collection, add UofL logo, clarify "up to" 3 year participation)	0.298	jja233	7/15/2022 5:22:53 PM
Informed ConsentParental Permission	Aim4_Additional Caregivers_CLEAN_7.15.22.pdf	Aim 4 additional caregiver CLEAN COPY	0.221	jja233	7/15/2022 5:15:03 PM
DataCollection	Medical Record Extraction Form.docx		0.031	jja233	7/15/2022 5:07:34 PM
DataCollection	SALT transcription.pdf		0.222	jja233	7/15/2022 5:01:57 PM
DataCollection	CELF Preschool.pdf		18.063	jja233	7/15/2022 5:01:40 PM
DataCollection	MacArthur-Bates - Words and Gestures.pdf	MacArthur Bates - Words & Gestures	0.567	jja233	7/15/2022 5:01:03 PM
Advertising	PUBHLTH-033c_flyer-UK&UofL_STAMPED.pdf	Recruitment flyer adding UofL/Norton logo - PR stamped	0.245	jja233	5/12/2022 3:46:56 PM
AdditionInfoConsiderations	[name] IAA with UoL.pdf	IAA with UofL	0.042	smcgo0	4/6/2022 8:11:31 AM
Advertising	Recording transcript submitted to IRB.docx	Recruitment video script	0.032	jja233	3/23/2022 10:05:23 AM
Waiver	HIPAA WAIVER OF AUTHORIZATION_updated 1.10.22.pdf	HIPAA Waiver of Authorization - updated 1.10.22	0.152	jja233	1/10/2022 8:37:44 AM

Advertising	Recruit ltr UK ENT_tracked changes 12.22.21.docx	Recruitment letter UK ENT (tracked changes)	0.032	jja233	12/22/2021 11:45:38 AM
Advertising	Recruit ltr UK ENT_clean 12.22.21.docx	Recruitment letter UK ENT (clean)	0.030	jja233	12/22/2021 11:45:14 AM
DataCollection	TAI_add qual response.pdf	TAI with additional open-ended comment question	0.235	jja233	12/21/2021 1:38:41 PM
DataCollection	PMI - revised CLEAN.docx	Revised PMI - clean	0.027	jja233	9/30/2021 9:00:56 PM
DataCollection	PMI - revised for CHAMPS-DHH due to control group.docx	Revised PMI - marked	0.029	jja233	9/30/2021 9:00:28 PM
DataCollection	FCU6-10 redcap.pdf	FCU survey (6+yrs)	0.144	jja233	9/30/2021 8:47:10 PM
DataCollection	FCU3-5 redcap.pdf	FCU survey (3-5yrs)	0.122	jja233	9/30/2021 8:46:48 PM
DataCollection	Locator Form_CLEAN 9.30.21.docx	Locator Form - clean copy 9.30.21	0.048	jja233	9/30/2021 4:41:50 PM
DataCollection	Locator Form_MARKED 9.30.21.docx	Locator Form - tracked changes 9.30.21	0.054	jja233	9/30/2021 4:41:21 PM
Advertising	IRB flyer explanation.pdf	explanation of additional images used on recruitment flyers	1.043	jja233	4/12/2021 11:46:27 AM
Advertising	PUBHLTH-033a_flyer PR edit STAMPED.pdf	Recruitment flyer - PR stamped	0.216	jja233	4/12/2021 11:46:01 AM
Advertising	CHAMPS DHH Facebook Post STAMPED.pdf	social media text	0.048	jja233	4/12/2021 11:44:58 AM
ResearchProcedures	REDCap Screenshots eConsent.docx	REDCap e-consent screenshots	0.330	jja233	2/26/2021 7:25:13 PM
Advertising	Recruit ltr OCSHCN_relaunch.docx	Recruitment letter OCSHCN	0.028	jja233	2/26/2021 12:59:41 PM
DataCollection	Data Collection Checklist_Baseline.docx	Data collection checklist example - baseline	0.036	jja233	2/26/2021 11:09:44 AM
DataCollection	Coach checklists combined_3.9.20.pdf	Checklists for FCU sessions	0.179	jja233	3/9/2020 1:27:38 AM
DataCollection	Supervisor log.docx	Clinical supervisor monthly time log	0.015	jja233	3/9/2020 1:20:33 AM
-Letter of Support & Local Context	UK Communication Plan Form between UK and UCDenver - [name] IAA 45213.pdf	UK - CU Communication Plan	0.307	crclar0	12/11/2019 11:35:32 AM
-Letter of Support & Local Context	UK.UCD.[name].pdf	University of Colorado local context	0.232	crclar0	12/11/2019 11:35:03 AM
-IRB Authorization Agreement	[name] IAA CHFS.pdf	IAA for KY Cabinet for Health and Family Services	0.059	jja233	11/18/2019 4:25:40 PM
DataCollection	Coach timelog.pdf	Parent coach monthly time log	0.570	jja233	11/10/2019 6:23:12 PM
DataCollection	PPVT-5_FormB.pdf	PPVT-5 Form B	0.796	jja233	11/10/2019 6:19:57 PM
DataCollection	PPVT-5_FormA.pdf	PPVT-5 Form A	0.679	jja233	11/10/2019 6:17:04 PM
DataCollection	Vineland-3.pdf	Vineland-3	1.815	jja233	11/10/2019 6:16:46 PM
DataCollection	MAB_W&S.pdf	MacArthur Bates - Words and Sentences	0.544	jja233	11/10/2019 6:16:29 PM
DataCollection	CBCL 6-18.pdf	CBCL Ages 6-18	0.237	jja233	11/10/2019 6:15:49 PM
AdditionInfoConsiderations	[name] IAA between UK and KH&V (KH&V relying).pdf	IAA for Kentucky Hands & Voices	0.200	jja233	11/4/2019 8:58:53 AM

🔗	DataCollection	Focus Group - Hearing Healthcare, SLP, DHH educator.pdf		0.066	crclar0	5/22/2019 3:18:04 PM
🔗	DataCollection	PSAT FINAL.pdf		0.147	crclar0	5/22/2019 3:16:58 PM
🔗	DataCollection	TSI_CHW post intervention.pdf		0.020	cbco233	5/21/2019 11:38:58 AM
🔗	DataCollection	FCU_COACHRatingForm - for binder.pdf		0.224	cbco233	5/21/2019 11:38:48 AM
🔗	DataCollection	PCIS - FINAL - post-training CHWs.pdf		0.029	cbco233	5/21/2019 11:36:39 AM
🔗	DataCollection	CASES FINAL - pre and post training and post intervention CHWs.pdf		0.205	cbco233	5/21/2019 11:36:30 AM
🔗	DataCollection	EBPAS-50_FINAL - pre training and post intervention.pdf		0.194	cbco233	5/21/2019 11:36:21 AM
🔗	DataCollection	Training or Practice Acceptability FINAL - post-training.pdf		0.044	cbco233	5/21/2019 11:36:11 AM
🔗	DataCollection	Interventionist Demographics Questionnaire FINAL.docx		0.033	cbco233	5/21/2019 11:36:01 AM
🔗	DataCollection	DPICS.pdf		0.159	cbco233	5/21/2019 11:18:57 AM
🔗	DataCollection	BIT.pdf		0.056	cbco233	5/21/2019 11:18:25 AM
🔗	DataCollection	GFTA.pdf		0.930	cbco233	5/21/2019 11:18:15 AM
🔗	DataCollection	Clinical Evaluaiton of Language Fundamentals 5.pdf		2.574	cbco233	5/21/2019 11:18:00 AM
🔗	DataCollection	Ling Sounds Test.docx		0.013	cbco233	5/21/2019 10:52:26 AM
🔗	DataCollection	FCU Feedback Form -Rainbow Sheet.pdf		0.204	cbco233	5/21/2019 10:52:11 AM
🔗	DataCollection	MAIS.pdf		0.286	cbco233	5/21/2019 10:48:34 AM
🔗	DataCollection	BDI-II.pdf		0.111	cbco233	5/21/2019 10:36:37 AM
🔗	DataCollection	PSCS.pdf		0.220	cbco233	5/21/2019 10:36:14 AM
🔗	DataCollection	PARYC.pdf		0.183	cbco233	5/21/2019 10:36:00 AM
🔗	DataCollection	CBCL.pdf		0.065	cbco233	5/21/2019 10:35:46 AM
🔗	DataCollection	Semistructured interview guide for parents.docx		0.015	cbco233	5/21/2019 10:34:43 AM
🔗	GrantContract	Research Strategy final.pdf	NIH Research Strategy	0.870	jja233	7/26/2018 2:00:05 PM

	AddInfoProduct	Fully executed MOU Aim 3 UKPH CCSHCN V12P.pdf	Aim 3 - fully executed MOU between UK and CCSHCN	0.211	jja233	6/14/2018 11:48:20 AM
	AddInfoProduct	Fully Executed MOU Aim 2 UKPH CCSHCN V12P.pdf	Aim 2 - fully executed MOU between UK and CCSHCN	0.039	jja233	6/14/2018 11:47:16 AM

Study Title: Behavioral Parent Training for Families With Deaf and Hard of Hearing Preschoolers

NCT Number: NCT03916146

## Statistical Analysis Plan

All tests will be two-sided with a 5% significance level and will be conducted in SAS. Analysis methods will account for clustering within parent coaches (i.e., statistical correlation among the outcomes from participants who share the same interventionist). Therefore, analysis of our primary outcome (parenting behaviors as measured by PARYC score at the first 6-month follow-up) will be achieved with linear mixed-effects modeling, with random effects to account for this clustering. A fixed effect for trial arm (FCU-DHH vs. TAU) will be the primary covariate of interest. Additional analyses will address each outcome over time (i.e., PARYC scores, PARCHISY scores, measures of child behavior, parent report and objective adherence with HA/CI, and language development). In longitudinal analyses, linear mixed effects modeling will be adjusted to account for the additional level of correlation among outcomes from the same subject (e.g., a random time effect or an unstructured covariance). Fixed effects will include trial arm, time (categorical or continuous variable), and their interaction, with the interaction being of primary interest. Because rolling study enrollment is necessary, some parent–child dyads may have fewer observations than others. Recommended statistical approaches will be used for missing data within interventionists (e.g., multiple imputation at the subject and cluster level). Sensitivity analyses will be considered and dictated by the type of missing data. We will measure potentially important predictors (e.g., sex, race, parental age, socioeconomic status, degree of hearing loss, type of hearing rehabilitation device, and baseline language development) and statistically compare the balance of the two trial arms. Secondary analyses will include these variables as covariates. Stratified randomization (by device type and poverty level) will be accounted for in analyses.

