## SECTION 2. Assessment and Evaluation of the Risks

For details, refer to the UK IRB's [Policy on Children in Research](#).

A. Provide justification for the participation of children as research subjects in your study.

The purpose of the study is to assess the effects of an adapted evidence-based parenting intervention on parent behaviors, child behaviors, child adherence to wearing their hearing equipment, and child speech/language outcomes. For all four outcomes, participation of the children is needed in assessment of outcomes, including videotaped tasks, parent-report measures, and measures administered directly to children. Children's direct participation in the parenting intervention is not necessary.

B. Has this research been conducted in adults? ☒ Yes ☐ No

If yes, is there any indication that the proposed research would benefit, or at least not be harmful to children?

There are 40 years of research evidence demonstrating the benefits of evidence-based parenting interventions to children and families.

C. Indicate how many children you propose to enroll in the study:

**Note:** Whenever possible, involve the fewest number of children necessary to obtain statistically significant data which will contribute to a meaningful analysis relative to the purpose of the study.

Justify this number:

Two children have already participated in Aim 3, the piloting of trial procedures. We plan to enroll 125 parent-child dyads (125 parents, 125 children; 72 dyads randomized to the intervention and 53 dyads randomized to the control condition) in the effectiveness trial, Aim 4. This number was determined by our biostatistician based on the individually-randomized trial design,  $\alpha=.05$ , the potential of clustering at the interventionist level, and the need to detect a medium-sized effect on the primary outcome (parenting behaviors).

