minutes); the 24-item PARYC (10 minutes); the 19-item PSCS (5 minutes); the 21-item BDI-II (5 minutes); the 25-item PMI (10 minutes); and the MacArthur Bates Words & Sentences form (20 minutes) or the MacArthur Bates Words & Gestures form (20 minutes) for children who do not yet produce 10 or more spoken words. Parents will also participate in a structured interview with the data collector to complete the Meaningful Auditory Integration Scale (MAIS); these assessments will be recorded and independently scored by research staff. Parents and children will complete four standardized Family Interaction Tasks (FIT) at baseline and annual assessments which will be videotaped and coded by two observers using (1) the DPICS coding system to provide an additional objective measure of parenting behaviors, and (2) the Systematic Analysis of Language transcripts (SALT) system for assessment of child language production. For families in the FCU-DHH condition, the FIT videos will also be used by parent coaches in feedback sessions. To increase retention during the study, we will also ask parent participants to complete a "Locator Information" form during baseline and annual assessments. The form lists alternative methods that parents agree can be used to locate them if their primary contact information changes or becomes disconnected during the study. During the initial informed consent process, the participant will indicate whether or not they choose to provide this information via an initialed checkbox on the consent document. If yes, either: a) the online survey will be programmed to display the Locator Form questions; b) the data collector will provide the Locator Information form in the mailed packet; or c) the data collector will ask for that information in a phone call. Any data received by mail will be entered into and stored in REDCap, which will be consulted to determine whether or not to provide copies of the Locator Information Form at follow-up assessments. Both the informed consent document and the text at the top of the locator form emphasize that completing the form is optional. If a research staff member uses this form to locate a participant by contacting a relative/friend listed by the participant, care will be taken to only indicate that we are trying to locate the individual in relation to a study. There will be no disclosure of the nature of the study, and therefore, no disclosure of the child's hearing loss.

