Aim 4 data analyses: To make trial arm (FCU-DHH vs. TAU) comparisons, we will utilize linear mixed modeling. In the models, we will utilize random effects corresponding to the interventionists, thus accounting for the possibility of clustering of outcomes from parent-child dyads who received the intervention from the same person. For the analysis of our primary outcome (parenting behaviors as measured by PARYC score at the first 6-month follow-up), a fixed effect for trial arm (FCU-DHH vs. TAU) will be the primary covariate of interest. Additional analyses for Hypotheses 1-4 will address each outcome over time (i.e., PARYC scores as well as continuous measures of child behavior, parent-report and objective adherence with HA/CI, and language development). To account for the correlation among repeated measurements from the same subject, in addition to random effects corresponding to the interventionists, we will also utilize an unstructured within-subject covariance structure. In these multilevel models, trial arm, time (categorical), and their interaction will be used as predictors, with the interaction being of primary interest. All tests will be two-sided with a 5% significance level and will be conducted in SAS Version 9.4 or higher (SAS Institute, Cary, NC). Furthermore, analyses will be based on intention-to-treat.

Principal components analysis and z-scores may be used to create composite language outcomes at each time-point due to the multiple measures proposed, which may reflect a single common trait. 100 Note that because rolling study enrollment is necessary (especially in smaller clinics), some parent-child dyads may have fewer observations than others.

We will measure potentially important predictors (e.g., sex, race, parental age, socioeconomic status, degree of hearing impairment, type of hearing rehabilitation device, baseline language development), and statistically compare the balance of the two trial arms. Secondary analyses will include these variables as covariates within the previously described models.

Prior to analyses, we will inspect variable distributions using histograms, probability plots, and residual plots. If necessary, transformations will be performed to make the variable distributions approximate a normal distribution. Alternatively, generalized estimating equations (GEE) may be utilized.

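### Baseline PARYC, completed by every parent before randomisation, is not pre-specified in the primary 6-month PARYC model, which gives up precision and leaves chance baseline imbalance in the estimate

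*Combined protocol and SAP*

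**What the plan says.** The SAP states that "analysis of our primary outcome (parenting behaviors as measured by PARYC score at the first 6-month follow-up) will be achieved with linear mixed-effects modeling"; clustering by parent coach is handled through random effects. It then says: "A fixed effect for trial arm (FCU-DHH vs. TAU) will be the primary covariate of interest". Its last sentence adds that the stratification by device type and poverty level will be accounted for. The protocol (Research Procedures, Aim 4 data analyses) gives the same primary model in almost the same words: "a fixed effect for trial arm (FCU-DHH vs. TAU) will be the primary covariate of interest".

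Both documents list potentially important predictors as examples. In the SAP they are "sex, race, parental age, socioeconomic status, degree of hearing loss, type of hearing rehabilitation device, and baseline language development". They serve to compare the balance of the arms, and then: "Secondary analyses will include these variables as covariates". Baseline PARYC is not among them.

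The score is available. The protocol's Aim 4 description of parent measures has all parents complete a baseline battery that includes "the 24-item PARYC (10 minutes"). Subject Children, Section 2, says that families were randomised once their baseline assessments were complete. That section also gives the sizing: 125 dyads, 72 to FCU-DHH and 53 to TAU, based among other things on "the need to detect a medium-sized effect on the primary outcome (parenting behaviors").

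PARYC over time, with arm, time and their interaction, is planned as an additional analysis.

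**The concern.** The baseline value of the outcome is usually an informative predictor of its follow-up value. Here it is collected from everyone, before allocation, at no further cost. A primary model without it has a wider confidence interval than the data allow. It also leaves in the estimate whatever difference in parenting scores the arms happened to start with, and stratifying by device type and poverty level does not control that difference.

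The covariate choice is odd as well. The example list names baseline language development, whose directly administered measures were taken at baseline only for families enrolled after the 3/2/2023 modification. It does not name the baseline of the primary outcome.

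If the decision is left open until the data are seen, there will be an adjusted and an unadjusted primary result to choose between.

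**Working it through.** **Inputs from the documents.** 72 and 53 dyads (Subject Children, Section 2); two-sided 5% (SAP); 10 coaches (protocol, Aim 5), hence 72/10 = 7.2 dyads per coach.

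**Assumptions, because the documents are silent.** Standardised effect d = 0.5 for a medium effect; 80% power as a benchmark; ICC 0 or 0.05, in the FCU-DHH arm only; loss 0 or 15% in both arms; correlation r between baseline and 6-month PARYC of 0.3 to 0.7.

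**The plan's own figure.** The 125 cannot be reproduced from what is stated. At d = 0.5 and 80% power, 1:1 allocation needs 2 × (2.802/0.5)² = 62.8, so 63 per arm and 126 in all. That is close to 125 but ignores clustering, loss and the unequal split. At 72:53 the control arm needs (2.802/0.5)² × (1 + 53/72) = 54.5, so 55 with 75 treated, 130 in all.

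**Formulas** (outcome SD = 1; nT and nC are the numbers analysed):
- Unadjusted variance = ICC/10 + (1 − ICC)/nT + 1/nC
- Adjusted variance = ICC/10 + (1 − ICC − r²)/nT + (1 − r²)/nC
- Power from the noncentral t with nT + nC − 2 degrees of freedom and noncentrality 0.5/SE
- Effect detectable with 80% power = 2.802 × SE

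**Worked case, ICC 0.05, no loss.**
- Unadjusted: 0.00500 + 0.01319 + 0.01887 = 0.03706; SE 0.193; power 73%.
- r = 0.3: 0.00500 + 0.86/72 + 0.91/53 = 0.03411; SE 0.185; power 77%.
- r = 0.7: 0.00500 + 0.46/72 + 0.51/53 = 0.02101; SE 0.145; power 93%.

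**Power**

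| Scenario | Unadjusted | r = 0.3 | r = 0.5 | r = 0.6 | r = 0.7 |
|---|---|---|---|---|---|
| ICC 0, no loss | 78% | 82% | 89% | 93% | 97% |
| ICC 0.05, no loss | 73% | 77% | 83% | 88% | 93% |
| ICC 0.05, 15% missing | 67% | 71% | 78% | 83% | 89% |

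At ICC 0.05 without loss, the detectable effect falls from 0.54 SD to 0.52 SD (r = 0.3) and to 0.41 SD (r = 0.7). Adjusted power there reaches 80% at about r = 0.4.

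**Other form of the adjustment.** Multiplying the whole variance, coach component included, by (1 − r²) and using the normal approximation gives 74% unadjusted and 78–95% adjusted at ICC 0.05 without loss. The picture is the same.

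**Equivalent sample.** With no clustering and r = 0.5, an adjusted analysis needs 125 × (1 − 0.25) ≈ 94 dyads for the precision that 125 give unadjusted.

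**Chance imbalance.** The standard error of the baseline difference between arms is √(1/72 + 1/53) = 0.18 SD. At r = 0.5, an imbalance of that size moves the unadjusted estimate by 0.5 × 0.18 = 0.09 SD, against an assumed effect of 0.5 SD.

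**The case against.** **A reader might infer that the plan rules baseline PARYC out.** It does not. Calling arm the primary covariate of interest leaves room for other covariates, the SAP itself later adds the strata, and the predictor list is given as examples. This is silence, not exclusion. What remains is that neither document commits to the term.

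**A reader might infer that the trial loses precision it was sized to need, or falls short of its intended power.** That cannot be shown. No target power, numeric effect, ICC, attrition or correlation is stated, and the sizing may or may not have assumed baseline adjustment. Under the assumptions above, but without clustering or loss, the unadjusted shortfall against 80% is only 1 to 2 points (78.3% by t, 78.9% by the normal approximation).

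**A reader might infer bias.** Under randomisation the unadjusted contrast is unbiased. Only efficiency and chance imbalance are at issue.

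**Baseline PARYC may enter the longitudinal model.** If baseline is one of its time points, that model can give a baseline-referenced 6-month contrast. But it is an additional analysis, its time points are not listed, and it does not replace the primary contrast. It does mean that no separate baseline term need be requested for the other outcomes, which are analysed only in such models.

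**The inputs are soft.** No document supports a value of r. At r = 0.3 the gain is about 4 points and does not reach 80% once there is clustering. The number of coaches may change, since replacements are allowed, and 15% missing is treated as data lost although the SAP mentions multiple imputation. These objections bear on the size of the gain, not on its direction.

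**Conclusion.** The point holds as an omission: the primary 6-month model does not pre-specify baseline PARYC, although the score is collected from all parents before randomisation. The consequence is lost precision and uncorrected chance imbalance. Validity is not affected, and no failure of the sample size has been shown.

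The omission can be read directly from the documents. The power figures are conditional on d = 0.5, 10 coaches and the assumed ICC, loss and r. Over r = 0.3 to 0.7 the gain is about 4 to 22 percentage points, depending on the scenario. For any non-trivial r, adjustment improves precision at a cost of about one degree of freedom. It does not guarantee 80% power: at ICC 0.05 with 15% missing, r = 0.5 still gives only 78%.

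**What to change.** In the SAP, and in the protocol's Aim 4 data analyses, state that the primary 6-month model includes baseline PARYC as a fixed covariate beside device type and poverty level. Alternatively, take the 6-month contrast from a longitudinal model that includes baseline with a common baseline mean in both arms; this also keeps dyads who lack the 6-month form.

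The cost is one sentence and one model term, with no new data and no burden on families. There is one condition. The protocol says funding ends in May 2025, and the latest attachments are dated September 2025, so the 6-month data have probably been collected. The change is credible only if it is fixed and dated before any unblinded analysis of the outcome.
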